This study will require a total of 140 children ages 6 to 18 years with asthma. The NIH requirement for distribution by ethnicity (33% ethnic minority) will be followed. Enrollment will be monitored so that a target of 40-50% females is reached. The rapidity of recruitment is greatly facilitated by the involvement of five geographically dispersed study sites. Patients will be recruited from the "standing" populations of the participating centers, by advertisement, and by referral from participating physicians. The CARE Data Coordinating Center (DCC) will distribute monthly accrual reports for each clinical center, listing patients entered and reasons for exclusion of potential subjects during the assessment/characterization period. This routine monitoring will allow early identification and resolution of potential problems in recruitment.

C. Study Visits

1. Week -1 Visit 1
 - a. Informed consent (parent's consent and child's assent) including consent for blood sample from parents to obtain genetic analysis
 - b. Review inclusion and exclusion criteria
 - c. Physical Examination
 - d. Exhaled nitric oxide
 - e. Forced oscillation
 - f. Inhaler technique reviewed and rescue medication (albuterol) dispensed
 - g. Maximal bronchodilator testing with spirometry. Forced oscillation after maximal bronchodilator response.
 - h. Electronic peak flow meter dispensed and appropriate technique assured
 - i. Determine personal best peak flow
 - j. Blood sample for complete blood count with hematocrit, total eosinophil count, IgE, ECP, chemistry and genetics analysis from participant. Arrange to obtain blood sample from both parents for genetic analysis.
 - k. Urine pregnancy test for female patients who have reached menarche
 - l. Urinary leukotriene measurement
 - m. Teach medication technique
 - n. Diary instructions provided and diary dispensed
2. Week 0 (Randomization) Visit 2
 - a. Subject returns 5 to 10 days after Visit 1

- b. Review inclusion and exclusion criteria
 - c. Exhaled nitric oxide
 - d. Spirometry for baseline FEV₁ value followed by methacholine challenge
 - e. Administer Asthma Control Questionnaire and modified Asthma Therapy Assessment Questionnaire
 - f. Allergen skin tests
 - g. Symptoms and peak flow meter readings on diary reviewed
 - h. Inhaler and electronic peak flow meter techniques reviewed
 - i. Compliance reviewed for diary card and peak flow meter recordings
 - j. Review diary card instructions and dispense diary cards

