Salmeterol, formoterol	≥48 hours
Anticholinergics	≥6 hours
Short-acting theophylline (e.g. Slophyllin tablets)	≥2 weeks
Long-acting theophylline (e.g. Theo-Dur, Slo-bid)	≥2 weeks
Ultra long-acting theophylline (e.g. Theo-24, Uniphyl)	≥2 weeks
Anticonvulsants (carbamazepine, phenobarbital, phenytoin)	≥4 weeks
Macrolide antibiotics	≥4 weeks
Rifampin, ketoconazole, sibutramine (Meridia)	≥4 weeks
Drugs to be withheld prior to pulmonary function, methacholine challenge, and/or skin testing per MOP	Specified time period
Antihistamines (except cetirizine and hydroxyzine – see below)	≥48 hours
Cetirizine*	≥3 days
Hydroxyzine	≥3 days
Methylxanthine-containing foods or beverages (e.g. coffee, tea)**	≥4 hours
Alcohol-containing foods or beverages	≥8 hours
*Cetirizine may be used during the study for treatment of allergic rhinitis but should be withheld prior to methacholine challenge testing per the MOP.	
**The washout period for these substances is recommended, but visits can continue if these substances have been used within the washout period.	

C. Criteria for Assigning Treatment Failure During Treatment Period

1. Use of systemic corticosteroids
2. Use of inhaled corticosteroids or leukotriene modifiers other than study medication
3. Hospitalization due to asthma

4. Hypoxic seizure due to asthma
5. Intubation due to asthma

D. Criteria for Assigning Drop-out Status During Treatment Period

1. Parent withdraws consent or child withdraws assent.
2. Patient becomes pregnant

V. Outcome Variables

A. Outcome Measures of Response

Pre- and post-bronchodilator spirometry, as well as functions obtained by forced oscillation, will be measured prior to and following each treatment interval. The primary outcome variable will be the change in pre-bronchodilator FEV₁ at the end of the active treatment period compared to the measure at randomization (Visit 2).

Several additional measures of asthma response will be employed in this trial. Patients will provide information on symptoms and rescue inhaled bronchodilator (albuterol) requirements at telephone calls and clinic visits. An Asthma Control Questionnaire and a modified Asthma Therapy Assessment Questionnaire (ATAQ) (53) will be administered every four weeks during the protocol. Symptom-free days will be incorporated as well as measurement of pharmaco-economic parameters. In addition, daily peak flow and FEV₁ measures will be collected using an electronic peak flow meter (Jaeger AM1[®]).

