The 5- to 10-day assessment/characterization period is considered the baseline period. Descriptive statistics at baseline will be calculated for continuous variables (means and standard deviations, or medians and inter-quartile ranges) and categorical variables (frequencies). The

descriptive statistics will be calculated based on the entire sample size and also according to sequence allocation.

The primary response variable in the CLIC trial is the change from baseline, defined as the pre-bronchodilator/pre-methacholine FEV₁ obtained at Visit 2, with respect to pre-bronchodilator FEV₁ (L) obtained at the end of each treatment period (Visits 4 and 6). The primary statistical analysis will examine this response on a continuous scale. Therefore, a mixed-effects linear model will be applied to account for the repeated measurements feature of the crossover design, such that the expected value of the response depends on the sequence and period of the crossover design (73):

	Period #1 (8 weeks)	Period #2 (8 weeks)
Sequence #1	$\mu_{LTRA} + v + \rho$	$\mu_{ICS} + v - \rho$
Sequence #2	$\mu_{ICS} - v + \rho$	$\mu_{LTRA} - v - \rho$

In the above table of expected values, μ_{LTRA} represents the population mean for active LTRA, μ_{ICS} represents the population mean for active ICS, v represents the population sequence effect, and ρ represents the population period effect. If there is a common carryover effect in this design, it is absorbed into the period effect. Note that the design contains no placebo wash-out periods. It was deemed necessary to exclude placebo wash-out periods because of ethical concerns. Therefore, the first four weeks of each treatment period will serve as pseudo wash-out periods. Outcome measurements taken during these pseudo-wash-out periods will not be included in the statistical analyses. Nevertheless, it will be of interest to conduct secondary comparisons that contrast the 4-week response to the 8-week response.

Restricted maximum likelihood (REML) estimation will be applied to estimate all of the model parameters via PROC MIXED of SAS 8.2.

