The statistical model described above also will be applied to the secondary outcome variables, which include β -adrenergic agonist use, symptom scores, FEV₁ bronchodilator reversibility, post-bronchodilator FEV₁, peak expiratory flow rate with treatment, peak expiratory flow variation, peak expiratory flow reversibility with bronchodilator, airway resistance by forced oscillation, and exhaled nitric oxide.

Research Aim 1 of the CLIC trial is to determine if the ICS and the LTRA are independent with respect to the primary outcome variable (the change from baseline with respect to pre-bronchodilator FEV₁). To pursue this objective, it is necessary to assess how each individual subject responds to the ICS and LTRA treatments. This is not straightforward within the context of the crossover design. However, an unbiased estimate of a subject's response within a particular period of the crossover design is constructed as the observed response minus the REML estimates of the nuisance parameters in that period. Correlation coefficients (Pearson, Kendall) then can be constructed, along with their 95% confidence intervals, to assess whether the responses to ICS and LTRA are independent (74). Similar analyses will be applied to the secondary outcome variables as well. In addition, exploratory analyses will be conducted in which the primary response (the change from baseline with respect to pre-bronchodilator FEV₁) is characterized as poor, marginal, or good. Various cutpoints will be attempted, such as response < 5% (poor), 5% ≤ response < 10% (marginal), response ≥ 10% (good). With respect to the exploratory analyses, Kendall correlation coefficients are preferred because they are better suited for ordinal data.

Research Aims 2 and 3 of the CLIC trial are to identify subgroups and asthma phenotypes and genotypes that are predictive of response (the change from baseline with respect to pre-bronchodilator FEV₁) for ICS and LTRA. **Research Aims 2 and 3** are exploratory in nature, but will yield useful information in determining subgroups of children who may or may not respond well to the active treatments. The statistical analyses will consist of two stages, with univariate analyses in the first stage and multivariate analyses (multiple regression) in the second stage. Candidate variables will include demographics, asthma phenotypes, and asthma genotypes. PROC FREQ and PROC UNIVARIATE of SAS 8.2 will be used for the univariate statistical analyses.

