Because of the possibility of drop-outs and other missed visits, there will be some missing data. The missing data complicate the planned statistical analyses for the specific aims, described above. With respect to the first specific aim, all available data will be included in calculating the correlation coefficients. For data that are missing, values can be imputed to generate the most extreme cases and the correlation coefficients can be determined under these circumstances. This approach will yield lower and upper boundaries for the estimated correlation coefficients and their confidence limits. In addition, a multiple imputation procedure will be implemented in order to account for the variability that occurs when replacing missing data with imputed values.

With respect to the second specific aim, the statistical analyses in the presence of drop-outs and missed visits is more complex, especially for the bivariate logistic regression analysis with generalized estimating equations (GEE). GEE requires that any missing data satisfy the assumption of "missing completely at random" (MCAR), i.e., the probability of response is independent of the observed and unobserved data (76). The MCAR assumption will be investigated and if it appears that it is violated, then likelihood-based regression models will be

implemented that assume either that the data are “missing at random” (MAR) or are non-ignorable (76).

G. Interim Analyses

The CLIC trial is not a typical effectiveness trial comparing treatments, so formal statistical analyses to evaluate effectiveness at interim time points will not be scheduled. However, an interim statistical analysis to evaluate the safety of the ICS and the LTRA will be scheduled at the midpoint of the trial and the results presented to the Data and Safety Monitoring Board (DSMB). The DSMB also will receive any reports of serious adverse events as they occur throughout the course of the trial.

H. Sample Size Justification

The target sample size for this trial is $N = 140$, and the justification is as follows. With respect to **Research Aim 1**, to test the null hypothesis that the Kendall correlation coefficient is zero versus a specified alternative at significance level α and statistical power $1 - \beta$, the approximate sample size formula is

$$N = 4(z_{1-\alpha/2} + z_{1-\beta})^2 / 9\tau^2$$

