where $z_{1-\alpha/2}$ and $z_{1-\beta}$ represent appropriate percentiles from the standard normal distribution (77). For a two-sided, 5% significance level test with 90% statistical power ($\alpha = 0.05$ and $\beta = 0.10$) against the alternative that $\tau = 0.2$, the required sample size is $N = 117$. However, to account for a maximum of 15% drop-outs and/or missed visits, it is necessary to increase the sample size to $N = 140$.

With respect to the exploratory statistical analyses planned for **Research Aims 2 and 3**, the sample size of 140 is in effect. The target sample size of $N = 140$ is chosen because it provides a 95% confidence interval with endpoints ± 0.15 for a Pearson-type correlation when the true correlation is 0.5 or greater and there is a maximum of a 15% drop-out rate. Although logistic regression analyses will be applied in addition to linear regression analyses (which yield Pearson-type correlations), the estimated parameter coefficients from a maximum likelihood algorithm in a logistic regression model will behave in a similar manner.

A sample size of $N = 210$ would provide a tighter 95% confidence interval than with $N = 140$, with endpoints ± 0.10 for a Pearson-type correlation when the true correlation is 0.5 or greater. Therefore, it may be desirable to recruit this larger number of subjects, if possible.

Recruitment will be monitored to determine whether it is feasible to pursue this larger sample size.

XII. Significance

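### Both drug responses subtract the same Visit 2 FEV₁, so a Kendall correlation of zero is not what unrelated drug effects imply, and the Aim 1 test rejects too often by an amount the protocol does not determine

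*Protocol*

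**What the plan says.** Section V.A takes FEV₁ "at the end of the active treatment period compared to the measure at randomization (Visit 2"). Section XI.D repeats this: "The primary response variable in the CLIC trial is the change from baseline, defined as the pre-bronchodilator/pre-methacholine" FEV₁ at Visit 2, set against the values at Visits 4 and 6. Each child therefore has two changes and one baseline reading.

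For Aim 1, Section XI.D takes each child's observed response in a period and subtracts only the REML estimates of the nuisance parameters. It then computes Pearson and Kendall coefficients with 95% confidence intervals "to assess whether the responses to ICS and LTRA are independent".

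Section XI.H bases the Aim 1 sample size on a wish "to test the null hypothesis that the Kendall correlation coefficient is zero versus a specified alternative". "For a two-sided, 5% significance level test with 90% statistical power" against τ = 0.2 it obtains N = 117, and "to account for a maximum of 15% drop-outs and/or missed visits, it is necessary to increase the sample size to" 140. It also gives a second basis for 140: a confidence interval of ±0.15 for a Pearson-type correlation under Aims 2 and 3.

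The text contains no second baseline, error correction or shifted null for Aim 1.

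**The concern.** A single spirometry reading differs from a child's usual level by some visit-to-visit error. If the Visit 2 reading happens to be low, the child appears to gain on both drugs. If it happens to be high, the child appears to lose on both. This alone makes the two changes move together across children, even when the drug effects are unrelated.

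Section XII says the trial will show whether response to one medication is independent of response to the other. A significant positive coefficient would be read as children responding to both drugs or to neither. Part or all of it could come from the shared reading, which could also mask the discordant responders whom Sections VI.G and XII hope to find. The exploratory poor/marginal/good classification uses the same baseline.

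**Working it through.** **The plan's own figure.** N = 4(1.960 + 1.282)² / (9 × 0.2²) = 116.7, so 117. Allowing for 15% loss, 117 / 0.85 = 137.6, so 138, close to the stated 140. Evaluable pairs: 140 × 0.85 = 119. The arithmetic is sound; the question is the null.

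**Model.** Write Visit 2 = U + e₀, end of ICS = U + d₁ + e₁, end of LTRA = U + d₂ + e₂. U is the child's level, the errors are independent with variance σ², and the true drug effects are unrelated with variance δ².

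- Covariance of the two changes = Var(e₀) = σ²
- Variance of each change = 2σ² + δ²
- Expected correlation ρ = σ² / (2σ² + δ²)
- Under normality, τ = (2/π) arcsin ρ

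Sequence and period terms are group means and leave e₀ in place. Section XI.D's description of the corrected response as unbiased concerns its mean, not the covariance of two responses sharing a reading.

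**Inputs for size.**
- SD of change: 13.52%, from the paediatric montelukast study in Section VI.G, read as an SD and assumed for ICS too. 13.52² = 182.8.
- Within-child SD of FEV₁ (σ): not in the protocol. Assumed 3% to 8%. The ceiling under this model is 13.52/√2 = 9.56%.

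With the SD of change fixed, ρ = σ²/182.8. False rejection is from simulation of the two-sided 5% Kendall test at 119 pairs, centred within sequence and period.

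| Assumed σ | ρ | Spurious τ | False rejection (nominal 5%) |
|---|---|---|---|
| 3% | 0.05 | 0.03 | about 8% |
| 4% | 0.09 | 0.06 | about 15% |
| 5% | 0.14 | 0.09 | about 30% |
| 6% | 0.20 | 0.13 | about 53% |
| 7% | 0.27 | 0.17 | about 80% |
| 8% | 0.35 | 0.23 | about 95% |

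Hand check at 5%, inverting the protocol's formula: 1.5 × √119 × 0.087 − 1.96 = −0.53, a probability of about 0.30.

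**What does not help.**
- Autocorrelated errors: with δ = σ, correlation of 0.3 or 0.5 between successive visits still gives 96% or 94% rejection (94% with independent errors).
- Adjusting for Visit 2 FEV₁: with an assumed between-child SD of 15%, rejection stays at about 25, 44, 68 and 87% for σ of 5, 6, 7 and 8%.
- More children: at the optional 210 (about 178 evaluable), rejection rises from 68% to 85% when δ = 1.5σ.

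**Separate baselines.** Using Visit 1 for one drug and Visit 2 for the other, with independent errors, mean τ is 0.00 and rejection is 4% to 5%. If Visit 1 and Visit 2 errors are correlated, bias returns. Across σ of 3% to 8%, rejection is about 5% to 20% at correlation 0.3 and 5% to a little over 40% at 0.5.

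**Power.** A latent τ of 0.2 corresponds to a Pearson correlation of sin(0.1π) = 0.309 between true effects. With separate baselines the observed correlation is 0.309 × δ²/182.8. At σ = 5%, δ² = 182.8 − 50 = 132.8, so ρ = 0.224 and τ = 0.144. Then 1.5 × √119 × 0.144 − 1.96 = 0.40, or about 65% power. Simulation gives about 84, 74, 63, 49, 33 and 16% for σ of 3% to 8%, with repeat runs differing by up to about three points.

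**The case against.** **Estimand.** Section XI.D defines Aim 1 in terms of the observed change from baseline, and for observed changes τ = 0 is a legitimate null. A design without placebo periods cannot isolate pure drug effects in any case. The second part stands: drift common to both periods would remain even with perfect spirometry. The first does not rescue the plan, because Sections XI.D and XII interpret the coefficient as independence of response to the two medications.

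**Size.** The protocol gives no within-child SD. The 13.52% comes from a montelukast study with mean FEV₁ of 72% predicted, whereas this trial excludes only values below 70% and stratifies at 85%. The primary response is also in litres. All of this stands: the direction is algebraic, the size is conditional.

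**Stronger readings.** A reader might infer that the test is bound to reject, or that the design can never produce τ = 0. Neither follows. At a within-child SD of 3% rejection is only about 8%. A negative association between the true effects of −σ²/δ² cancels the bias exactly: −25/132.8 = −0.19 at 5% and −36/110.8 = −0.32 at 6%. A reader might also infer that 140 has no other support, but Section XI.H gives the ±0.15 interval as a second basis.

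**Remedy.** Visit 1 is not a clean replicate. It precedes Visit 2 by only 5 to 10 days, its reversibility result can decide eligibility (Section IV.A), and time of day is matched to Visit 2 only (Section III). These limits stand and must accompany the fix.

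**Conclusion.** The point holds as a fault in the Aim 1 null and in its interpretation. With unrelated drug effects the expected correlation of the two changes is σ²/(2σ² + δ²), above zero, and nothing in the protocol removes it. Type I error therefore exceeds 5%. On the assumptions above it lies between about 8% and 95% for a within-child SD of 3% to 8%, and the protocol does not say where in that range the trial falls. The stated 90% power at τ = 0.2 applies to the correlation of observed changes, not of drug effects.

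The documents do not support extending this to the treatment comparison. The mean ICS–LTRA contrast is unaffected, because the common baseline cancels within each child. The three-category analysis is affected too, but the protocol labels it exploratory.

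**What to change.** 1. Report the common-baseline coefficients as descriptive, and do not read them against zero as a test of independence.
2. Add an Aim 1 estimate with Visit 1 pre-bronchodilator FEV₁ as a second baseline. Section III.C lists "Maximal bronchodilator testing with spirometry" at that visit, and the reversibility criterion in Section IV.A requires a pre-bronchodilator value. Either use Visit 1 for one drug and Visit 2 for the other, swap and average, or correct the covariance by an error variance estimated from the Visit 1–Visit 2 pair.
3. Obtain confidence intervals by bootstrapping children, and give a sensitivity range for the correlation between Visit 1 and Visit 2 errors.
4. State the limits: residual upward bias from correlated errors, possible regression to the mean from Visit 1 eligibility testing, unmatched time of day at Visit 1, and drift common to both periods.
5. Restate the Aim 1 power as applying to observed changes, and give the lower power against a latent τ of 0.2.

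No new visit or measurement is needed. The cost is analysis wording and programming, plus open acknowledgement that 140 children may give well under 90% power for the question Aim 1 asks.

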A multivariate analysis will be applied in the second stage, such as a bivariate multiple regression analysis for the continuous outcome (the change from baseline with respect to pre-bronchodilator FEV₁) and bivariate logistic regression for the categorical version of the response that uses generalized estimating equations (75). PROC MIXED and PROC GENMOD of SAS 8.2 will be used for these statistical analyses.

Changes to the protocol's eligibility criteria as approved by the Data Safety Monitoring Board and the five clinical sites are anticipated on August 1, 2002. These include 1) allowing either the demonstration of reversibility or a methacholine PC₂₀ ≤ 12.5 mg/ml to qualify subjects, 2) increasing the maximum allowed albuterol use during the assessment/characterization period from once per day on average to four times per day on average, excluding pre-exercise albuterol

use, 3) no longer excluding patients who have a borderline increase in liver enzymes, and 4) no longer excluding patients with morbid obesity. Subjects will be classified according to whether they are eligible under the original entry criteria or the revised entry criteria. Then, the statistical analysis will include a blocking factor to account for this classification.

E. Drop-out Status

Drop-out status is assigned to any randomized child (1) who requires systemic corticosteroids for an asthma exacerbation, (2) who requires another corticosteroid (other than the study ICS or maintenance intranasal corticosteroid) for any illness, (3) who becomes pregnant, (4) who withdraws assent, or (5) whose parent withdraws consent.

If a child is assigned drop-out status, then only that child's data prior to drop-out status will be included in the primary statistical analyses. If a child reaches drop-out status, then the primary outcome variable for any ensuing active treatment period cannot be assessed properly, so these data are excluded. Although this statistical approach is not congruent with an intent-to-treat philosophy, it is warranted because this is an efficacy trial and not an effectiveness trial. The specific aims of the CLIC trial are to characterize children's responses to the active ICS and the LTRA treatments.

F. Missing Data

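### Protocol XI.D excludes the Week 4 FEV1 (Visits 3 and 5) from the analyses, not only from the endpoint, so as written it cannot serve as auxiliary information when a Week 8 value is missing

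*Protocol*

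**What the plan says.** Protocol XI.D defines the primary response as the change in pre-bronchodilator FEV1 from Visit 2 to the end of each treatment period, Visits 4 and 6. There is no placebo wash-out, so "the first four weeks of each treatment period will serve as pseudo wash-out periods". The next sentence is the rule at issue: "Outcome measurements taken during these pseudo-wash-out periods will not be included in the statistical analyses". One use is then allowed: "Nevertheless, it will be of interest to conduct secondary comparisons that contrast the 4-week response to the 8-week response".

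XI.E assigns drop-out status to a child who, among other reasons, needs systemic corticosteroids for an exacerbation. For such a child "then only that child's data prior to drop-out status will be included in the primary statistical analyses", and later active periods are excluded.

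XI.F deals with missing values for the first aim, the ICS-LTRA correlation. It plans extreme-case bounds, and also "a multiple imputation procedure will be implemented in order to account for the variability that occurs when replacing missing data with imputed values". It names no predictors. For the second aim it foresees that data may not be missing completely at random.

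Section III.C places Visits 3 and 5 at Week 4 of their periods, with spirometry at both. Section V.A adds daily home FEV1 and peak flow.

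**The concern.** The exclusion refers to the statistical analyses in general and is not limited to the primary response. Because the 4-week response has to be let back in as an exception, the Week 4 visits evidently count as excluded. An analysis plan that followed the sentence could not use the Visit 3 or Visit 5 FEV1 to inform a missing Visit 4 or Visit 6 value.

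That matters because one route to drop-out is an exacerbation needing systemic corticosteroids. A child doing poorly on the current drug at Week 4 may be likelier to be lost before Week 8. A likelihood or imputation analysis corrects for this only if the variables that predict loss are in the model. The same child's clinic FEV1, on the same drug four weeks earlier, is an obvious candidate. Without it, the drug with more such losses looks better than it is.

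Wash-out is also a weak reason for excluding the value in period 1. Entry already requires at least 4 weeks off inhaled corticosteroids and 2 weeks off leukotriene modifiers before Visit 1, and no study drug precedes that period.

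**Working it through.** **1. The plan's own figure (XI.H).** N = 4(z₀.₉₇₅ + z₀.₉₀)² / (9τ²) with τ = 0.2 gives 116.75, rounded up to 117, as stated. Then 117/0.85 = 137.6, so 138; the protocol uses 140. With 15% loss, 140 × 0.85 = 119 evaluable children, and power by the same formula is 90.5%. The stated Aim 1 power does not depend on Week 4 data.

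**2. What Week 4 data could add to Aim 1.** Approximate effective N = 119 + 21 × s × r². Here 21 = 140 − 119, s is the share of those children who have a Week 4 value, and r is the Week 4-Week 8 correlation (both assumed).
- s = 1, r = 0.5 to 0.9: effective N 124 to 136, power 91.7% to 93.8%. A direct simulation gave about 123 to 134.
- s = 0.25: effective N 120 to 123, power 90.8% to 91.5%.

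The gain is about 3 percentage points of power at most.

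**3. Bias in the treatment means (XI.D mixed model).**
- From the protocol: N = 140 (XI.H); montelukast change 8.23%, SD 13.52% (VI.G, the paediatric trial).
- Assumed: ICS mean 10%, so the true difference is 10 − 8.23 = 1.77; between-drug correlation 0.3; Week 4-Week 8 correlation 0.5, 0.7 or 0.8; logit of loss = a − 1.2 × standardised Week 4 change.
- Method: normal-theory maximum likelihood on the two Week 8 values alone, or with the two Week 4 values added. Each setting used 300 to 400 trials; Monte Carlo SE was about 0.07 to 0.08 points.
- Two separately coded runs. In run B a child lost in period 1 also lost period 2.

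Loss mostly on LTRA, estimated ICS-LTRA difference (true 1.77), at correlation 0.5 / 0.7 / 0.8:

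| Run | Incomplete pairs | Without Week 4 | With Week 4 |
|---|---|---|---|
| A | about 11% | 1.39 / 1.19 / 1.04 | 1.82 / 1.86 / 1.83 |
| B | about 12% | 1.32 / 1.06 / 0.91 | 1.83 / 1.75 / 1.78 |

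The shortfall without Week 4 is 1.77 − 1.39 = 0.38 at the least and 1.77 − 0.91 = 0.86 at the most.

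Loss on both drugs (about 13% incomplete): the LTRA mean was overstated by 0.3 / 0.5 / 0.7 points (A) or 0.54 / 0.72 / 0.92 (B) without Week 4, and by about 0.1 or less with it. In run B the difference stayed essentially unbiased, so the ICS mean was overstated by a similar amount. The Aim 1 correlation moved by about 0.01. Completely random loss gives no bias.

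**4. Scale.** With SD 13.52 and correlation 0.3, the within-child difference has SD 13.52 × √(2 × 0.7) = 16.0. With 119 pairs its standard error is 16.0/√119 = 1.47. A bias of 0.38 to 0.86 is therefore about 0.26 to 0.59 of a standard error.

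**The case against.** The strongest reply is that the sentence only protects the outcome model from carry-over, and that the imputation predictors belong in an analysis plan that is not shown. XI.F neither names nor forbids any. In part this stands: the effect on imputation is an inference from the breadth of XI.D's wording. But XI.D states a rule rather than leaving a gap, and an analysis plan that complied with it could not use these values. It can also be said that Visits 3 and 5 sit on the boundary of the four weeks and may fall up to 7 days later. The exception for the 4-week response answers that.

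Stronger readings are tempting and should be resisted:
- **A contradiction with XI.E.** A reader might infer that XI.D deletes data that XI.E promises to keep. It does not. A child lost between Visits 3 and 4 lacks a primary value because the response is defined only at Visits 4 and 6. A child lost after Visit 5 still contributes Visit 4.
- **Nothing left from the broken-off period.** Home FEV1, peak flow and diary data after Week 4 are outside the exclusion and could inform imputation. Nor do the documents show that Week 4 clinic FEV1 is the best predictor.
- **Material damage to Aim 1.** XI.F ties multiple imputation to that aim, where the effect is negligible. The bias point belongs to the XI.D mixed model.

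The simulation also favours the fix by design. Loss depends only on Week 4 FEV1, so including it makes the loss ignorable, and every lost child has a Week 4 value. Loss before Week 4 or unrelated to FEV1 gains nothing. The paediatric montelukast trial cited in VI.G lost 6% and 7% of its two groups, less than the 11-12% assumed. The SD is for percent change, while the primary response is in litres.

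**Conclusion.** The point holds in a limited form. XI.D's exclusion is wider than its purpose needs: as written, it bars the Visit 3 and Visit 5 clinic FEV1 as auxiliary information as well as from the endpoint. If loss depends on Week 4 FEV1 and falls mainly on one drug, the ICS-LTRA mean difference can be biased by roughly 0.4 to 0.9 percentage points, in favour of the drug with more losses. That rests on the assumed loss mechanism, 11-12% incomplete pairs and a Week 4-Week 8 correlation of 0.5 to 0.8. Similar loss on both drugs leaves the difference nearly unbiased. The figures show a possible size and do not predict this trial's error. The change is worth making because it makes missing-at-random more credible at almost no cost.

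**What to change.** In XI.D, replace the exclusion sentence with: *Visit 3 and Visit 5 measurements are not endpoints but may be used as auxiliary information.* Keep the 4- versus 8-week comparison as it is.

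In XI.F, include the same-period Visit 3 or Visit 5 FEV1 change, with treatment and sequence, in the imputation model.

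At least as a sensitivity analysis, fit the mixed model to Visits 3 to 6 with a separate mean for each sequence and visit and an unstructured covariance. Read the contrast at Visits 4 and 6 only: average Visit 6 minus Visit 4 in sequence 1 with Visit 4 minus Visit 6 in sequence 2. In XI.D's notation these are μ_ICS − μ_LTRA − 2ρ and μ_ICS − μ_LTRA + 2ρ, so the period effect cancels. Separate means keep any residual first-drug effect on the Visit 5 mean out of the Week 8 contrast.

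Cost: wording, slightly more analysis work and some extra parameters (an unstructured covariance has 4 × 5/2 = 10 for four visits, against 2 × 3/2 = 3 for two). No new data are needed and the endpoint is unchanged.
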